8 DESCRIPTION OF VISITS

Below are the visits and the interventions that may occur at each of the visits. In addition to the following scheduled visits, we are also including an unscheduled visit that may be used for any reason when a subject needs to return to the study site to complete study activities.

Visit 0 (Screening Visit)

1. Review the study with the subject and obtain written informed consent and HIPAA authorization
2. Assign the subject a unique subject id number
3. Complete asthma control test and asthma control questionnaire
4. Record demographics and other baseline data

5. Record medical and surgical history, including a history of asthma, diagnosis date, and asthma signs and symptoms
6. Record concomitant medications
7. Review inclusion/exclusion criteria
8. Measure and record height and weight without shoes
9. Perform and record vital signs, including blood pressure after the subject has been seated for 5 minutes
10. Perform and record oximetry
11. Perform abbreviated physical exam
12. Obtain urine to perform urine pregnancy test (when applicable) and urine cotinine test
13. Obtain blood for prostate specific antigen test (when applicable)
14. Perform spirometry with maximum bronchodilator response
15. Perform FeNO
16. Obtain blood
17. Record any adverse events (AEs) that may have occurred since signing consent
18. Schedule MCT or Visit 1

MCT Visit, if needed (Anytime between days 1-7, must be at least 3 days prior to Visit 1)

1. Confirm ongoing consent to participate
2. Collect urine for pregnancy test if applicable
3. Record vital signs and weight
4. Complete MCT checklist
5. Perform and record MCT
6. Confirm eligibility criteria
7. Record adverse events
8. Schedule Visit 1

Visit 1 (Day 7 ± 3)

1. Complete asthma control test and asthma control questionnaire
2. Review and record any changes to concomitant medications
3. Record any adverse events (AEs) that may have occurred since last visit
4. Measure and record weight without shoes
5. Perform and record vital signs, including blood pressure after the subject has been seated for 5 minutes
6. Perform and record oximetry
7. Perform abbreviated physical exam
8. Obtain urine to perform urine pregnancy test (when applicable)
9. Perform spirometry
10. Perform FeNO
11. Obtain blood
12. Give subject a dosing and symptom diary and instructions on dosing intervals
13. Randomize to receive placebo or DHEA-S
14. Send home with 28 days of DHEA-S or placebo capsules
15. Schedule visit 2

Visit 2 (Day 21 ± 3) phone visit

1. Complete asthma control test and asthma control questionnaire
2. Review and record any changes to concomitant medications
3. Record any adverse events (AEs) that may have occurred since last visit
4. Schedule visit 3

Visit 3 (Day 35 ± 3)

1. Complete asthma control test and asthma control questionnaire
2. Review and record any changes to concomitant medications
3. Record any adverse events (AEs) that may have occurred since last visit
4. Review inclusion/exclusion criteria
5. Measure and record weight without shoes
6. Perform and record vital signs, including blood pressure after the subject has been seated for 5 minutes
7. Perform and record oximetry
8. Perform abbreviated physical exam
9. Obtain urine to perform urine pregnancy test (when applicable)
10. Perform spirometry
11. Perform FeNO
12. Obtain blood
13. Collect any unused capsules from visit 1
14. Collect dosing and symptom diary
15. Schedule visit 4

Visit 4 (Day 63 ± 3)

1. Complete asthma control test and asthma control questionnaire
2. Review and record any changes to concomitant medications
3. Record any adverse events (AEs) that may have occurred since last visit
4. Measure and record weight without shoes
5. Perform and record vital signs, including blood pressure after the subject has been seated for 5 minutes
6. Perform and record oximetry
7. Perform abbreviated physical exam
8. Obtain urine to perform urine pregnancy test (when applicable)
9. Perform spirometry
10. Perform FeNO
11. Obtain blood
12. Give subject a dosing and symptom diary and instructions on dosing intervals
13. Randomize to receive placebo or DHEA-S (will enter whatever did not receive in visits 1-3)
14. Send subject home with 28 days of 100 mg DHEA-S or placebo capsules to take daily
15. Schedule visit 5

Visit 5 (Day 77 ± 3) phone visit

1. Complete asthma control test and asthma control questionnaire

2. Review and record any changes to concomitant medications
3. Record any adverse events (AEs) that may have occurred since last visit
4. Schedule visit 6

Visit 6 (Day 91 ± 3)

1. Complete asthma control test and asthma control questionnaire
2. Review and record any changes to concomitant medications
3. Record any adverse events (AEs) that may have occurred since last visit
4. Measure and record weight without shoes
5. Perform and record vital signs, including blood pressure after the subject has been seated for 5 minutes
6. Perform and record oximetry
7. Perform abbreviated physical exam
8. Obtain urine to perform urine pregnancy test (when applicable)
9. Perform spirometry
10. Perform FeNO
11. Obtain blood
12. Collect any unused capsules from visit 4
13. Collect dosing and symptom diary

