3 STUDY OBJECTIVES

3.1 PRIMARY OBJECTIVE:

- Determine if slow-release DHEA in patients with asthma improves quality of life based on ACQ/ACT scoring.

3.2 SECONDARY OBJECTIVE:

- Determine if slow-release DHEA increases FEV₁ in patients with asthma.
- Determine if SR DHEA in patients with asthma increases the change in pulmonary functions post maximum bronchodilator challenge.
- Determine if slow-release DHEA in patients with asthma decreases FeNO.
- Evaluate the safety and tolerability of DHEA in asthma.
 - Safety outcomes include changes in:
 - Adverse events (AEs)
 - Serious adverse events (SAEs)
 - Pulmonary function (FEV₁, FVC, FEV₁/FVC, FEF25-75)

(An asthma exacerbation (physician decision to treat) will be considered an event of particular interest. Exacerbations not admitted to the hospital will be considered an AE. Exacerbations requiring admission will be considered a SAE.)

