4.1 MULTIPLE DOSE STUDY

The dose of DHEA will be 100 mg via slow release (SR) capsules. Subjects will take one capsule daily at the same time each day.

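### Each period supplies 28 daily capsules, but the visit windows allow up to 34 days from dispensing to the end-of-period assessment, so Visits 3 and 6 can fall up to 6 dose-free days after the supply ends.

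*Protocol*

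**What the plan says.** Section 4.1 sets the regimen: "Subjects will take one capsule daily at the same time each day". Section 8 sets the supply. Visit 1, item 14 reads "Send home with 28 days of DHEA-S or placebo capsules", and Visit 4, item 14 reads "Send subject home with 28 days of 100 mg DHEA-S or placebo capsules to take daily".

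Sections 6 and 8 place the visits on study days counted from screening as Day 0, each with a ±3-day window: Visit 1 at Day 7, Visit 3 at Day 35, Visit 4 at Day 63 and Visit 6 at Day 91. Visits 1 and 4 are the dispensing visits. Visits 3 and 6 close the two periods with ACT/ACQ, spirometry, FeNO and blood. Visits 2 and 5 are by telephone and collect ACT/ACQ but no lung function or FeNO.

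At Visit 3 the instruction on returned drug is "Collect any unused capsules from visit 1", with a matching item at Visit 6. The protocol states no overage, resupply, first-dose day or last-dose rule, and does not require the subject to be on drug at Visits 3 and 6.

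**The concern.** The supply matches the nominal schedule exactly and leaves no margin for the late side of the protocol's own windows. Because the end-of-period window is counted from screening and not from the dispensing date, an early dispensing visit and a late closing visit add up. The subject then runs out of capsules before the assessment, with nothing recorded as a deviation.

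The outcomes most exposed are the secondary ones, FEV1 and FeNO; one objective is "Determine if slow-release DHEA in patients with asthma decreases FeNO". Each is measured during treatment once per period, at Visit 3 or Visit 6. If that visit falls after the supply ends, no other on-treatment value exists, and no analysis can recover one. The primary-objective scores, ACQ and ACT, are less exposed because they are also taken at the telephone visits. Their end-of-period values can still include untreated days: Section 7 describes the ACQ as covering 7 days, so in the extreme case six of those seven would be off drug.

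**Working it through.** **Inputs** (protocol Sections 4.1, 6 and 8): one capsule per day; 28 days' supply per period; Visit 1 on Day 4–10, Visit 3 on Day 32–38, Visit 4 on Day 60–66, Visit 6 on Day 88–94.

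**Nominal schedule.** 35 − 7 = 28 and 91 − 63 = 28. The supply fits the target days exactly.

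**Permitted gap from dispensing to closing visit.**

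| | Shortest | Longest |
|---|---|---|
| Period 1 | 32 − 10 = 22 | 38 − 4 = 34 |
| Period 2 | 88 − 66 = 22 | 94 − 60 = 34 |

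A Day 4 dispensing visit is feasible. The methacholine test must precede Visit 1 by at least 3 days, which a Day 1 test satisfies, and the test is done only in some subjects.

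**Dose-free days before the visit day**, for a fully adherent subject:
- first capsule on the dispensing day: max(0, gap − 28), at most 34 − 28 = 6;
- first capsule the next day: max(0, gap − 29), at most 34 − 29 = 5.

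Days treated before the visit run from 22 to 28 with a same-day first dose; the supply caps the upper end.

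**How often.** Let a and b be the offsets (−3 to +3) of the dispensing and closing visits, so gap = 28 + b − a over 7 × 7 = 49 combinations. The visit-timing distributions below are assumptions, because the protocol gives none. All treat a and b as independent.

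| Assumed timing | At least one dose-free day, same-day first dose | Same, next-day first dose |
|---|---|---|
| All visits on target | 0 | 0 |
| 80% on target, 3.33% on each other day | 0.177 | 0.119 |
| 70% on target, 5% on each other day | 0.248 | 0.168 |
| Uniform | 21/49 = 0.429 | 15/49 = 0.306 |

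Check of the 70% row: P(a = b) = 0.70² + 6 × 0.05² = 0.505, so P(b > a) = (1 − 0.505)/2 = 0.2475. P(b − a = 1) = 4 × 0.05² + 2 × 0.70 × 0.05 = 0.08, leaving 0.1675 for the next-day case.

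**Length of overrun** (same-day first dose): overruns of 1, 2, 3, 4, 5 and 6 days arise in 6, 5, 4, 3, 2 and 1 combinations. So 6 + 5 + 4 = 15 of the 21 are 1–3 days, and the 6-day extreme is 1/49 = 2% under uniform timing.

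**Telephone visits.** Visit 2 minus Visit 1 is 18 − 10 = 8 to 24 − 4 = 20 days; Visit 5 minus Visit 4 is 74 − 66 = 8 to 80 − 60 = 20 days. Both always fall within the supply.

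**The case against.** The strongest reply is that the schedule is coherent on target and fails only when tolerances stack in one direction. That is true; the windows permit the overrun without causing it. Visits 3 and 6 are also booked at the preceding telephone visit, when the dispensing date is known, at a single site with 30 subjects. A careful coordinator would avoid most overruns, and the independence assumed in the frequencies may then overstate them. This stands, and it is why the range starts at 0%.

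Other text softens the gap without closing it. Subjects receive dosing instructions at Visits 1 and 4 that are not reproduced in the protocol. The diary and the capsule return would show dose-free days after the fact. An unscheduled visit could carry extra supply, and the pharmacy prescription might include overage. None of these sets a rule, and a recorded gap still leaves no on-treatment FEV1 or FeNO.

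The effect is also limited. Dilution can arise only in the DHEA period, missed doses leave capsules over and shorten the gap, and 1–3 untreated days barely touch the 4-week recall of the ACT. These points stand as limits on size.

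Finally, dosing through to Visit 3 would remove dose-free days that now lengthen the washout. With Visit 1 on Day 4, Visit 3 on Day 38 and Visit 4 on Day 60, the last same-day-start dose is Day 31, which is 60 − 31 = 29 days before Visit 4; dosing to Visit 3 cuts this to 60 − 38 = 22. But the present plan already allows nearly that: with Visit 1 on Day 10, the last dose is Day 37 (Day 38 with a next-day start), 23 or 22 days before Visit 4.

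**Conclusion.** The concern holds. Following the stated supply and windows exactly can yield end-of-period values taken off drug, by up to 6 days (5 with a next-day first dose). This assumes the windows are read on study day, as written, and that the subject takes every capsule. The share of periods affected lies between 0% and 43% depending on visit timing. At 80% on target it is 12–18%, or 30 × 0.119 ≈ 4 to 30 × 0.177 ≈ 5 of the 30 planned DHEA periods if all subjects complete.

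The direction of the effect is towards diluting the DHEA–placebo contrast, chiefly for FEV1 and FeNO. Its size cannot be given, because the protocol states no offset time for slow-release DHEA. This does not undermine the design, but it is an avoidable weakness that should be corrected.

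**What to change.** State the day of the first dose, then adopt one of two options.

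- **Option A: more capsules.** Dispense 35 per period (the longest permitted gap of 34 days plus the visit day) and continue dosing until the visit. This costs 7 more capsules per period. Days treated before the visit would range from 22 to 34, and the added doses can shorten the washout as described above.
- **Option B: re-anchor the visits.** Count Visits 3 and 6 from the actual dispensing date with no late side, for example 25 to 28 days after dispensing. With a same-day first dose this holds days treated to 25–28 and leaves no dose-free day before the visit. The latest Visit 3 is still Day 10 + 28 = 38, so the shortest interval to Visit 4 stays at 60 − 38 = 22 days. The cost is slightly less scheduling flexibility.

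Option B is the cleaner choice, since it also narrows the spread in exposure. Re-anchoring while keeping ±3 days is not enough: it allows 28 + 3 = 31 days, and so up to 3 dose-free days. Either option needs only a short protocol amendment.

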9 STUDY RISKS

DHEA: DHEA is commercially available without a prescription. The DHEA capsules used in this study are formulated for slow release. Most of the known data pertaining to risks come from studies in adults with adrenal insufficiency who were treated with long courses of DHEA (e.g. 3-12 months). Many of these trials were included in a recent meta-analysis (27). This paper included 10 trials where 264 women treated with 20-50mg (most were 50mg) daily for 3-12 months (most were 4-6 months). None of the trials reported any serious adverse effects from prolonged therapy with DHEA. Minor side effects reported include greasy skin, hirsutism, acne, scalp itching and increased sweating. In two trials including 36 men, reported side effects included diarrhea (n=1), mild acne (n=1) and increased facial hair (n=1) (28, 29). In a study of 23 adolescent girls and young women (ages 13-25) treated with 25mg of DHEA for 1 year, adverse events were similar between DHEA and placebo (30). One girl developed mild hirsutism, and no subjects developed acne. We are aware of a single case report of a 55-year-old patient developing palpitations after 2 weeks of DHEA therapy (50mg/day) that were found to represent premature atrial and ventricular contractions (PACs and PVCs) that resolved with an oral beta-blocker therapy (31). Finally, we recently completed a pilot study of DHEA repletion in female asthma patients with DHEA-S levels <200 µg/dl. The short-term (2 week) regimen was associated with a significant improvement in post-bronchodilator FEV₁, and no major side effects were observed (5). These results support feasibility of the proposed trial and suggest that asthma patients with low DHEA-S plasma levels will tolerate DHEA treatment.

Blood collection and genotyping: When blood samples are taken from a vein, subjects may have discomfort or pain where the blood was taken. Sometimes a person may become dizzy or faint when blood is taken. There is also a risk of infection (rare), bleeding, redness or bruising at the skin puncture.

Bleeding and bruising can usually be reduced by putting pressure on the place where the blood was taken. The chance of infection is lowered by using standard skin cleaning and sterile needles.

Genotype data is obtained from blood analysis. The only risk specifically associated with genotyping is breach of confidentiality. Every effort will be made to maintain confidentiality and all study data will be treated as confidential information. No identifiable information released or shared with individuals outside the study team.

Spirometry: There is a small risk of lightheadedness, wheezing, shortness of breath or increased cough when performing spirometry. These symptoms usually resolve quickly without the need for treatment. Withholding short-acting/long-acting beta-agonists prior to study visits: There is a risk of shortness of breath or breathing difficulty. Subjects will be advised that if they experience any worsening symptoms during the pre-visit withholding period, they should use their usual medication as needed and call the study team to cancel or reschedule the study visit.

Methacholine Challenge Test (MCT): The volunteer may experience coughing, chest tightness, shortness of breath, and/or wheezing during this procedure. These symptoms typically resolve spontaneously 10-15 minutes after testing without active intervention – recovery can be hastened as needed with administration of albuterol.

FeNO: Such testing can cause a subject to become light-headed, dizzy or tired. In asthmatic subjects, testing may also induce or worsen wheeze, shortness of breath, and/or chest tightness. Rescue therapy with Albuterol will be administered as needed. The chance of these symptoms occurring is low and treatment will be readily available.

Medication Withhold: Withholding medications may cause subjects to experience increased symptoms of the condition for which the medication is taken. Subjects will be advised that if they experience any unmanageable, worsening symptoms during the pre-visit withholding period, they should use their usual medication(s) as needed and call the study team to cancel or reschedule the visit.

Urine Collection: Urine will be collected by clean-catch. There are no foreseeable risks to its collection. However, there is the risk of emotional distress if a subject discovers that she is pregnant. Our study coordinators are highly trained and experienced regarding advising women who discover that they are pregnant as part of a research protocol.

Questionnaires: At any time during the study, subjects can stop answering or skip questions that feel too personal or make them uncomfortable.

10 STUDY BENEFITS

There are no expected direct benefits to individual subjects participating in this research. The information obtained from this research study may prove helpful for future asthma patients and other pulmonary research projects.

11 WITHDRAWAL FROM STUDY PARTICIPATION

An individual subject will be withdrawn from the trial if the subject withdraws consent (the subject is not required to justify this decision). All withdrawals will be documented and the reason (if provided) for withdrawal will be recorded. There is no need to follow subjects after withdrawal. If a subject wishes to withdraw consent, the PI will have his/her stored specimens discarded. Specimens already tested or used by another researcher will not be destroyed. Information already learned from the testing of the sample will not be destroyed. If a subject starts taking the DHEA-S or placebo and then calls in prior to completion of the study to say that they want to stop taking it/withdraw from the study, we will ask the subject to come back for their final lab draw and return their unused capsules.

In addition, a subject may be withdrawn from the study at any time if the PI feels that it is not in the subject's best interest to continue. Possible reasons for study withdrawal include but are not limited to:

- Subject withdrawal of consent
- Subject is not compliant with or tolerating study procedures
- Subject is not adherent to study drug schedule
- Adverse event that, in the opinion of the PI, places the subject at increased risk
- Lost to follow-up
- Physician request for early termination of study
- Subject becomes pregnant

Being a part of this clinical trial while pregnant may expose the unborn child to significant risks. Therefore, pregnant women will be excluded from the study. A pregnancy test will be done at the beginning at every study visit for any women of childbearing potential, and it must be negative before they can enter and continue in this study. All subjects must agree to use appropriate contraceptive measures during the study. Medically acceptable contraceptives include: (1) surgical sterilization, (2) approved hormonal contraceptives such as birth control pills, (3) barrier methods (such as a condom or diaphragm) used with a spermicide, (4) abstinence, or (5) an intrauterine device (IUD). If they become pregnant during this study, they must inform a member of the research team immediately. In this scenario, study drug will be discontinued immediately, and the subject will be monitored throughout the pregnancy and for 1 year after study drug was discontinued. The baby will be monitored for adverse events for 1 year after birth.

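### Section 11 merges stopping study drug with leaving the study and does not list the primary questionnaires for the early-stop visit, so end-of-period outcome data can be lost

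*Protocol*

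**What the plan says.** Four statements in Section 11 of the protocol bear on this point.

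- **Follow-up.** "There is no need to follow subjects after withdrawal". The sentence stands in the paragraph on withdrawal of consent, but it is worded for any withdrawal and comes directly after a sentence about documenting all withdrawals.
- **Withdrawal by the PI.** The sentence, cut here before its last word, reads "a subject may be withdrawn from the study at any time if the PI feels that it is not in the subject's best interest to". The possible reasons include "Subject is not adherent to study drug schedule", "Subject is not compliant with or tolerating study procedures" and "Adverse event that, in the opinion of the PI, places the subject at increased risk".
- **Stopping drug.** A subject who has started capsules and calls in "to say that they want to stop taking it/withdraw from the study" is handled as a single case. Apart from pregnancy, Section 11 describes no status for a subject who is off drug but still followed.
- **Return visit.** For that subject, "we will ask the subject to come back for their final lab draw and return their unused capsules". No questionnaire, spirometry or FeNO is named.

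The primary objective in Section 3.1 is: "Determine if slow-release DHEA in patients with asthma improves quality of life based on ACQ/ACT scoring". FEV₁, FeNO, and safety and tolerability are secondary (Section 3.2). Section 4 describes a cross-over, and Section 4.2 plans 30 subjects. The schedule in Section 6 has ACT and ACQ at every visit except the methacholine visit, including the phone contacts at Visits 2 and 5. Spirometry and FeNO are scheduled at Visits 0, 1, 3, 4 and 6.

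**The concern.** Adherence and adverse events arise after randomization and may depend on which capsule the subject is taking. Section 9 lists acne, greasy skin and hirsutism among the reported effects of DHEA, so stopping could plausibly be more common in the DHEA period than in the placebo period. If such subjects leave without an outcome assessment, those who remain are selected on something treatment may have influenced.

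A cross-over is particularly exposed. A subject who leaves during period 1 never contributes the second half of the within-person comparison, and with 30 subjects each lost pair counts. Subjects who stop early also carry much of the information for the tolerability objective.

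This is a data-collection rule, so it belongs in the protocol. An analysis plan can choose how to handle missing values, but it cannot supply questionnaires that nobody asked the subject to complete.

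**Working it through.** **Step 1. What is kept and what can be lost.** This follows from the visit schedule in Section 6. Capsules are dispensed at Visits 1 and 4, and the periods end at Visits 3 and 6.

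| Subject leaves between | ACT/ACQ kept | ACT/ACQ that may be lost | Spirometry and FeNO on treatment |
|---|---|---|---|
| Visits 1 and 2 | Visits 0, 1 | Visits 2–6 | none |
| Visits 2 and 3 | Visits 0–2 | Visits 3–6 | none |
| Visits 4 and 5 | Visits 0–4 | Visits 5, 6 | period 1 only |
| Visits 5 and 6 | Visits 0–5 | Visit 6 | period 1 only |

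A subject who leaves after Visit 5 still has mid-period ACT/ACQ from both periods. The first two rows have no period 2 data at all.

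**Step 2. Does another section fill the gap at the return visit?** Section 13 commits to ACT at each visit and to pulmonary function at the start of each visit. Read literally, that covers ACT and spirometry at an early return visit. Two things prevent it from settling the matter.

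- Section 13 names neither ACQ nor FeNO.
- Its wording cannot be literal. It also promises a physical exam at all visits, yet Visits 2 and 5 are phone contacts for which Sections 6 and 8 list neither an exam nor spirometry.

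Sections 11 and 13 therefore need reconciling.

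**Step 3. Illustrative loss of precision.** The protocol gives N = 30 but no alpha, power, SD, effect size or dropout rate, so there is no stated figure to reproduce. Assumptions: two-sided alpha 0.05, 80% power, a t-test on the within-person difference with n − 2 degrees of freedom, and each lost subject giving no usable pair. The detectable difference δ, in SD of the within-person difference, solves

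P(T′ > t₀.₉₇₅,ₙ₋₂) = 0.80, where T′ is noncentral t with n − 2 df and noncentrality δ√n.

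A close approximation is δ ≈ (t₀.₉₇₅ + t₀.₈₀)/√n. For n = 30 this is (2.048 + 0.855)/5.477 = 0.53.

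| Assumed loss | Pairs | δ | Power at δ = 0.53 |
|---|---|---|---|
| 0% | 30 | 0.530 | 80% |
| 10% | 27 | 0.561 | 75% |
| 20% | 24 | 0.598 | 70% |

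**Step 4. Illustrative bias if loss is informative.** Assume a true effect of zero, a completers-only analysis, and loss of the fraction d with the worst values of an index that has correlation ρ with the DHEA-minus-placebo difference. The bias in SD units is ρ·φ(c)/(1 − d), with c = Φ⁻¹(d).

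- d = 0.10: φ(c)/(1 − d) = 0.1755/0.90 = 0.195. For ρ = 0.25 to 0.5 the bias is 0.05 to 0.10 SD, and a nominal 5% test has a real error of about 6% to 8%.
- d = 0.20: 0.2800/0.80 = 0.350. The bias is 0.09 to 0.17 SD, and the real error is about 7% to 14%.

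Both d and ρ are assumptions. These figures show the scale of the risk and are not estimates for this trial.

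**The case against.** Much can be said for the protocol, and most of it limits the point without removing it.

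- **Withdrawal is discretionary.** The PI may withdraw a subject; nothing makes it automatic. A reader might infer that non-adherence always ends participation, but the text does not say so. This stands.
- **The tolerance item concerns study procedures.** Drug intolerance enters only through the adverse-event and adherence items. This stands.
- **The no-follow-up sentence may apply only to withdrawn consent.** Its placement supports that reading and its wording does not. It is ambiguous, and narrowing it costs nothing.
- **Nothing forbids collection.** A reader might infer that the protocol bars outcome data after stopping. The sentence only lifts an obligation. Section 8 allows unscheduled visits for any reason, and Section 14.4 allows case-by-case follow-up of adverse events. This stands, but data that nobody is instructed to collect will be collected unevenly.
- **No completers-only analysis is stated.** Section 17 says mixed-effects models for repeated measures will be considered, and these use partial data. This stands. Such models are unbiased only if the observed data explain the loss, which is doubtful when subjects leave over tolerability or adherence.
- **The section does not strictly contradict itself.** One close-out visit is compatible with no continuing follow-up. This stands.
- **Later scores are off drug.** After a period 1 stop, further questionnaires do not recreate an on-drug pair, and the ACT's 4-week recall mixes time on and off drug. This stands: the remedy reduces the loss and does not remove it.

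**Conclusion.** The point holds in a limited form. Section 11 gives no separate standing to a subject who stops capsules but would stay in the study, and it does not list the primary measure for the visit that subject is asked to attend. End-of-period ACT/ACQ, and all period 2 data for period 1 stoppers, can be lost as a result.

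It would be tempting to conclude that the data are lost in a treatment-related way. The documents do not support that as fact. Section 9 reports mainly minor effects, and one cited study of a lower dose found adverse events similar to placebo. Treatment-related loss is a plausible risk.

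The size is unknown because no dropout rate is given. The rise from 0.53 to 0.56–0.60 SD assumes 10% to 20% loss and the worst case in which a lost subject contributes nothing. That loss of precision is modest; possible bias is the larger reason to act. The change should be made, because it is cheap and the missing questionnaires cannot be recovered later.

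**What to change.** Amend Section 11 as follows.

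1. Define stopping study drug and withdrawing consent as separate events.
2. Limit the no-follow-up sentence to withdrawn consent.
3. For subjects who stop drug, or whom the PI withdraws, but who keep consent, list ACT and ACQ at the return visit already requested, with spirometry and FeNO if they attend.
4. Collect ACT and ACQ by phone at the remaining scheduled times, as is already done at Visits 2 and 5.
5. Record the date of last dose so that on-drug and off-drug scores can be told apart.
6. Align Section 13 with Section 11 on what is measured at an early return visit.

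The rules on when study drug stops are not touched.

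The cost is amendment wording and a few short questionnaires or calls for the subjects concerned. Scores obtained after stopping support an as-randomized comparison and not an on-drug one, so the analysis must state which it uses.
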